15.6. Subject Participation Card

The subject will be provided with a subject participation card bearing the following information:

- That he/she is participating in a clinical study (incl. study code)
- That he/she has been treated with the study drug
- The name and phone number of the investigator

The subject will be asked to keep the subject participation card in their possession at all times during the study and to return it at the last study visit, if applicable.

Include statement whether each subject's primary care physician will be notified of their participation in the study by the investigator, if the subject agrees.

15.7. Subject Confidentiality

Subject confidentiality is strictly held in trust by the participating investigators, their staff, and Hansa Biopharma and their agents. This confidentiality is extended to cover testing of biological samples and genetic tests in addition to the clinical information relating to participating subjects.

The study protocol, documentation, data, and all other information generated will be held in strict confidence. No information concerning the study, or the data will be released to any unauthorized third party without prior written approval of Hansa Biopharma.

The study monitor or other authorized representatives of Hansa Biopharma may inspect all documents and records required to be maintained by the investigator, including but not limited to, medical records (office, clinic, or hospital) and pharmacy records for the subjects in this study. The clinical study site will permit access to such records.

16. ARCHIVING

16.1. Retention of Clinical Study Site Documentation

The investigator is responsible for maintaining all the records, which enable the conduct of the study at the site to be fully understood, in compliance with ICH GCP. The study documentation including all the relevant correspondence should be kept by the investigator for at least 25 years *[or longer if so required by local law]* after the completion or discontinuation of the study, if no further instructions are given by Hansa Biopharma.

The investigator is responsible for the completion and maintenance of the confidential subject identification code which provides the sole link between named subject source records and anonymous CRF/eCRF data for Hansa Biopharma. The investigator must arrange for the retention of this Subject Identification Log and signed Informed Consent Documents for at least 25 years *[or longer if so required by local law]* after the completion or discontinuation of the study.

No study site document may be destroyed without prior written agreement between the investigator and Hansa Biopharma. Should the investigator elect to assign the study documents to another party, or move them to another location, Hansa Biopharma must be notified. If the investigator retires and the documents can no longer be archived by the site, Hansa Biopharma can arrange having the Investigator File archived at an external archive.

16.2. Study Master File

Hansa Biopharma will archive the Study Master File in accordance with ICH GCP and applicable regulatory requirements.

CI	Confidence Interval
CL	Total systemic clearance of drug
C _{max}	Maximum Serum Concentration
CRF	Case Report Form
CV	Coefficient of Variation
DSA	Donor Specific Antibody
ECG	Electrocardiogram
eGFR	estimated Glomerular Filtration Rate
FAS	Full Analysis Set
HLA	Human Leukocyte Antigen
HR	Heart Rate
IA	Immunoabsorption
IgG	Immunoglobulin G
IMP	Investigational Medicinal Product
LLQ	Lower Limit of Quantification
MDRD	Modification of Diet in Renal Disease Study
MedDRA	Medical Dictionary for Regulatory Activities
MFI	Mean Fluorescence Intensity
NCA	Non-Compartment Analysis
PCR	Polymerase Chain Reaction
PD	Pharmacodynamics
PE	Plasma Exchange
PK	Pharmacokinetics
PKS	Pharmacokinetic analysis set
PPS	Per-protocol Set
PT	Preferred Term
SAE	Serious Adverse Event
SAP	Statistical Analysis Plan
Screened	Patient who enters the screening phase of the study
SD	Standard Deviation
SE	Standard Error
SOC	System Organ Class
STDm	Study data Tabulation Model
TEAE	Treatment Emergent Adverse Event
TLF	Tables, Listings and Figures
T _{max}	Time of observed C _{max}

T _½	Elimination half-life
TM	Trial Master
Vz	Apparent Volume of Distribution during the terminal phase
WHO	World Health Organization

1 Introduction

This document describes the planned statistical analyses for 16-HMedIdeS-12 which will include data processing, data analyses and data presentation. This Statistical Analysis Plan (SAP) is based on the study protocol version 4.3, 5.3, 6.3, 7.3 and 8.3 (1). These are country-specific protocols for 5 different countries (France, Austria, US, Australia and Germany), allowing the countries to have minor differences regarding some exclusion criteria. These differences are deemed to not influence the analysis specified in this SAP.

1.1 Study objectives and endpoints

These are the objectives as stated in the protocols above.

1.1.1 Objectives

The primary objective of this study is to:

- Investigate the efficacy of imlifidase compared with plasma exchange (PE) in removal of Donor Specific Antibody (DSA) in patients who are experiencing an active or chronic active Antibody Mediated Rejection (AMR) episode after kidney transplantation

The secondary objectives of this study are to:

- Evaluate DSA levels up to 180 days after treatment
- Evaluate Human Leukocyte Antigen (HLA)-antibodies levels up to 180 days after treatment
- Evaluate the overall kidney function up to 180 days after treatment
- Investigate the occurrence of AMR up to 180 days after treatment
- Investigate the safety and tolerability of imlifidase compared to PE in patients experiencing active or chronic active AMR episodes
- Evaluate the number of PE-sessions needed
- Evaluate the pharmacokinetics (PK), pharmacodynamics (PD) and immunogenicity of imlifidase (ADA)

1.1.2 Endpoints

The primary endpoint of this study is:

- Maximum reduction in DSA level at any time point during the 5 days following the start of treatment

The secondary endpoints of this study are:

- DSA levels up to 180 days after treatment
- HLA-antibodies levels up to 180 days after treatment
- Kidney function change from baseline (at screening) as evaluated by estimated Glomerular Filtration Rate (eGFR), P-creatinine and albumin/creatinine ratio in urine up to 180 days after treatment

- Proportion of patients with graft loss within 180 days of treatment
- Signs of transplant glomerulopathy 180 days post treatment
- Change from baseline (at screening) in histopathology per Banff Criteria at 29 and 180 days
- Change from baseline (at screening) in mRNA levels in kidney biopsies evaluated by [REDACTED] [REDACTED] at 29 and 180 days from baseline. If kidney biopsy is performed before screening, mRNA levels will be evaluated on day 29 and day 180 (no baseline will be available)
- Safety parameters (adverse events [AEs], safety laboratory tests, vital signs and electrocardiogram [ECG])
- Type, frequency and intensity of adverse events
- Number of sessions with PE
- Total Serum Immunoglobulin G (IgG) levels over time
- Presence of intact IgG on SDS-page until start of IVIg treatment
- DSA functionality determined by C1q or C3d analysis pre- and post-treatment
- PK profile of imlifidase (C_{max} , T_{max} , $t_{1/2}$, AUC, CL, V_z)
- Presence of anti-implifidase IgG (ADA)
- Number of patients with resolution of AMR at day 180
- Patient survival at day 180

2 Study design

The study is a phase II, randomized, open-label, multi-centre study with an active control investigating the efficacy and safety of imlifidase compared with PE, in removing anti-HLA antibodies to treat active and chronic active AMR post-transplant. A total of 30 male and/or female patients will be included in the study. The 30 patients are planned to be distributed in 5 countries (France, Austria, US, Australia and Germany) and 14 sites.

DSA measurements and biopsies will be done at screening. If deemed eligible for the study during the screening visit, patients will be randomized in ratio 2:1 in the following way:

- 20 patients will be randomized to treatment with a single dose of 0.25 mg/kg imlifidase. The 20 patients will receive treatment with 0.25 mg/kg imlifidase at visit 2 (Day 1). On day 4 the 20 patients will be given high dose IVIg (may be given over 2 days). A single dose of rituximab will be given 5 days after completion of the high dose of IVIg. DSA will be measured at multiple timepoints during visit 2, and at all following visits. On day 29 and 180 kidney biopsies will be performed.
- 10 patients will be randomized to be treated with 5-10 sessions of PEs. The 10 patients will start the treatment with PEs at visit 2. After the last PE session, the 10 patients will be given high dose IVIg (may be given over 2 days). A single dose of rituximab will be given 5 days after completion of the high dose of IVIg. DSA will be measured at multiple timepoints during visit 2, and at all following visits. On day 29 and 180 kidney biopsies will be performed.

Figure 1 and 2 below shows a summarized outline in the study for the imlifidase arm and PE arm.

Figure 1: Overall study outline imlifidase arm

[figure not shown]
[figure not shown]

Figure 2: Overall study outline PE arm

2.1 Overview of study procedures

2.1.1 Flow Chart imlifidase arm

Table 1: Study flow chart imlifidase arm, Screening to End of Study

Visit Number	1	2	3	4	5	6	7	8	9	10	11
Type of visit	Screening	Treat-ment	Assessments								FU/End of study
Day		1-5	6	8	11	15	22	29	64	90	180
Assessment /Time window			0	0	±2d	±2 d	±3 d	±3 d	±7d	±7d	±14d
Informed Consent	X	See table 2									
Demographics	X										
Medical/surgical history, incl transplantation and previous AMRs	X										
Record historical creatinine values	X										
Record number of pregnancies (if applicable)	X										
Inclusion/exclusion criteria	X										
Randomization	X										
Physical examination	X										X
Height and weight	X										
Blood pressure and pulse rate	X			X	X	X	X	X	X	X	X
Respiratory frequency	X										
Body temperature	X			X	X	X	X	X	X	X	X
PCR test for SARS-CoV-2 virus	X										
ECG	X										X
Pregnancy test (serum)	X										X
Safety laboratory tests (incl creatinine for eGFR)	X			X	X	X	X	X	X	X	X
Urine sample for measurement of albumin/creatinine ratio	X			X	X	X	X	X	X	X	X
ADA (IgE)	X ^a										
DSA, incl HLA antibodies and functionality	X ^b			X	X	X	X	X	X	X	X
PK sampling				X	X	X	X				
PD sampling			X	X	X	X	X	X	X	X	

Visit Number	1	2	3	4	5	6	7	8	9	10	11
Type of visit	Screening	Treat-ment	Assessments								FU/End of study
Day		1-5	6	8	11	15	22	29	64	90	180
Assessment /Time window			0	0	±2d	±2 d	±3 d	±3 d	±7d	±7d	±14d
ADA(IgG)				X	X	X	X	X	X	X	X
Kidney biopsy	X ^c							X ^c			X ^c
Methylprednisolone /Prednisolone			Will be given according to treatment schedule (section 5.3 in protocols) and continue as long as prescribed by investigator								
Antibiotic prophylaxis			Treatment will continue until IgG levels return to acceptable values, as judged by the investigator								
Rituximab				X ^d							
Concomitant medication and other treatment	Throughout the study										
Adverse events	Throughout the study										

^{a)} Sample will be taken pre-dose but no need to wait for result before start of treatment

^{b)} One DSA sample will be sent to local lab for evaluation for inclusion and one DSA sample will be collected for central analysis at Hansa Biopharma

^{c)} One piece of tissue will be sent to local pathology lab and one piece of tissue will be sent for analysis at [REDACTED]. If kidney biopsy is performed prior to screening, a piece of tissue cannot be sent for [REDACTED] analysis unless site stores tissue in mRNA later as standard of care. Then the tissue may be sent for [REDACTED] analysis after informed consent is signed.

^{d)} Rituximab will be given 5 days after completed high dose of IVIg

Table 2: Study flow chart imlifidase arm, visit 2, treatment

Visit Number	2									
Time	Pre-dose	Treat-ment								
			30 min	1 h	2 h	6 h	24 h	48 h	72 h	96 h
Assessment /Time window			±10 min	±10 min	±15 min	±30 min	±2h	±2h	±6h	±6h
Blood pressure and pulse rate	X				X	X	X	X	X	X
Respiratory frequency	X						X	X	X	X
Body temperature	X						X	X	X	X
Safety laboratory tests (incl creatinine)							X	X	X	X
Methylprednisolone/ prednisolone ^a	X						X	X	X	X
Antihistamine	X									

Visit Number	2									
Time	Pre-dose	Treatment								
			30 min	1 h	2 h	6 h	24 h	48 h	72 h	96 h
Assessment /Time window			±10 min	±10 min	±15 min	±30 min	±2h	±2h	±6h	±6h
Antibiotic prophylaxis	X		Treatment will continue until IgG levels return to acceptable values, as judged by the investigator							
DSA, incl HLA antibodies and functionality	X				X	X	X	X	X ^b	X
PK sampling	X		X	X	X	X	X	X	X ^b	X
PD sampling	X				X	X	X	X	X ^b	X
ADA (IgG)	X						X			
P-creatinine (for calculation of eGFR)	X									
Urine sample for measurement of albumin/creatinine ratio	X						X	X	X	X
Imlifidase infusion		X								
High dose IVIg									X ^c	
Concomitant medication and other treatment	Throughout the visit									
Adverse events	Throughout the visit									

^{a)} Methylprednisolone/prednisolone will be given according to the treatment schedule in section 5.3 in the protocols

^{b)} Samples should be taken prior to start of high dose IVIg is given

^{c)} May be given over two days

2.1.2 Flow Chart PE arm

Table 3: Study flow chart PE arm, Screening to End of Study

Visit Number	1	2	3	4	5	6	7	8	9	10	11
Type of visit	Screening	Treatment	Assessments								FU/End of study
Day		1-5	6	8	11	15	22	29	64	90	180
Assessment /Time window			0	0	±2d	±2 d	±3 d	±3 d	±7d	±7d	±14d
Informed Consent	X	See									
Demographics	X										
Medical/surgical history, incl transplantation and previous AMRs	X										

Visit Number	1	2	3	4	5	6	7	8	9	10	11
Type of visit	Screening	Treat-ment	Assessments								FU/End of study
Day		1-5	6	8	11	15	22	29	64	90	180
Assessment /Time window			0	0	±2d	±2 d	±3 d	±3 d	±7d	±7d	±14d
Record historical creatinine values	X										
Record number of pregnancies (if applicable)	X										
Inclusion/exclusion criteria	X										
Randomization	X										
Physical examination	X										X
Height and weight	X										
Blood pressure and pulse rate	X		X	X	X	X	X	X	X	X	X
Respiratory frequency	X										
Body temperature	X		X	X	X	X	X	X	X	X	X
PCR test for SARS-CoV-2 virus	X										
ECG	X										X
Pregnancy test (serum)	X										X
Safety laboratory tests (incl creatinine for eGFR)	X		X	X	X	X	X	X	X	X	X
Urine sample for measurement of albumin/creatinine ratio	X		X	X	X	X	X	X	X	X	X
ADA (IgE)	X ^a										
DSA, incl HLA antibodies and functionality (if applicable, taken before PE)	X ^b		X	X	X	X	X	X	X	X	X
PK sampling			X	X	X	X					
PD sampling (if applicable, taken before PE)			X ^d	X ^{d,e}	X ^{d,e}	X	X	X	X	X	X
ADA(IgG)				X	X	X	X	X	X	X	X
Kidney biopsy	X ^c							X ^c			X ^c
Methylprednisolone /Prednisolone			Will be given according to treatment schedule (section 5.3 in protocols) and continue as long as prescribed by investigator								
Antibiotic prophylaxis			Treatment will continue until IgG levels return to acceptable values, as judged by the investigator								
High dose IVIg			High dose IVIg will be given after last PE session. Dose may be given over two days								
Rituximab				Will be given 3 to 4 days after completed high dose IVIg							

Visit Number	1	2	3	4	5	6	7	8	9	10	11
Type of visit	Screening	Treat-ment	Assessments								FU/End of study
Day		1-5	6	8	11	15	22	29	64	90	180
Assessment /Time window			0	0	±2d	±2 d	±3 d	±3 d	±7d	±7d	±14d
Concomitant medication and other treatment	Throughout the study										
Adverse events	Throughout the study										

- a) Sample will be taken pre-dose but no need to wait for result before start of treatment
 b) One DSA sample will be sent to local lab for evaluation of inclusion and one DSA sample will be collected for central analysis at Hansa Biopharma
 c) One piece of tissue will be sent to local pathology lab and one piece of tissue will be sent for analysis at [REDACTED]. If kidney biopsy is performed prior to screening, a piece of tissue cannot be sent for [REDACTED] analysis unless site stores tissue in mRNA later as standard of care. Then the tissue may be sent for [REDACTED] analysis after informed consent is signed.
 d) If high dose IVIG is given, the PD sample must be taken prior to IVIG.
 e) If high dose IVIG is completed and there is no scheduled PD sample at the latest the following day, an additional PD sample will be taken

Table 4: Study flow chart PE arm, visit 2, treatment

Visit Number	2									
Time	Pre-dose	Treat-ment								
			30 min	1 h	2 h	6 h	24 h	48 h	72 h	96 h
Assessment /Time window			±10 min	±10 min	±15 min	±30 min	±2h	±2h	±6h	±6h
Blood pressure and pulse rate	X				X	X	X	X	X	X
Respiratory frequency	X						X	X	X	X
Body temperature	X						X	X	X	X
Safety laboratory tests (incl creatinine)							X	X	X	X
Methylprednisolone/prednisolone ^a	X						X	X	X	X
Antibiotic prophylaxis	X		Treatment will continue until IgG levels return to acceptable values, as judged by the investigator							
DSA, incl HLA antibodies and functionality (if applicable, taken before PE)	X				X	X	X	X	X	X
PK sampling	X				X	X	X	X	X	X
PD sampling functionality (if applicable, taken before PE)	X				X	X	X	X	X	X
ADA (IgG)	X						X			

Visit Number	2									
Time	Pre-dose	Treatment								
			30 min	1 h	2 h	6 h	24 h	48 h	72 h	96 h
P-creatinine (for calculation of eGFR)	X									
Urine sample for measurement of albumin/creatinine ratio	X						X	X	X	X
PE		X								
Concomitant medication and other treatment	Throughout the visit									
Adverse events	Throughout the visit									

- a) Methylprednisolone/prednisolone will be given according to the treatment schedule in Section 5.3 in section 5.3 in the protocols

2.2 Determination of sample size

No formal calculation has been done for the sample size. A sample size of totally 30 patients is chosen where 20 patients are treated with imlifidase and 10 patients are treated with PE.

The standard deviations for the two previous studies 14-HMedIdeS-04 and 15-HMedIdeS-06 can be considered to argue for the sample size of 30 patients. The standard deviations for the reduction of the IgG were 6% in the 14-HMedIdeS-04 and 4% in the 15-HMedIdeS-06 study. If the standard deviations are assumed to be similar in this study, it will give approximately an 8% point wide Confidence Interval (CI) when the sample size on 10+20 patients are considered. The 8% point wide of the CI is an acceptable wide and therefore the sample size on 30 patients can be used.

2.3 Blinding

The study is an open-label study. The study is fully unblinded.

2.4 Randomisation

The 30 patients will be allocated to the treatments by using block randomization. The randomizing will be 2:1 where 20 patients are treated with imlifidase and 10 patients are treated with PE. No stratification is used in this study.

2.5 Data pre-processing

The export data sets from the Larix data management Trial Master (TM) will be transformed into Study Data Tabulation Model (SDTM) structure and format following the implementation guide version 3.3 (current version) and also following “Therapeutic Area Data Standards User Guide for Kidney Transplant Version 1.0 (Provisional)”. Analysis Data Model (ADaM) data sets will be prepared based on the SDTM data sets following implementation guide version 1.1 (current version). Tables, figures, and listings will be prepared from the ADaM data sets.

3 Analysis sets

Every patient will be classified according to the below definitions of the Full analysis set (FAS), Per-Protocol analysis set (PPS), Safety analysis set (SAF) and Pharmacokinetic analysis set (PKS). The analysis sets will be determined at the data review prior to database lock. Decisions will be documented in the database lock minutes.

3.1 Full Analysis Set

FAS will consist of all patients treated with any amount of study medication. Patients will contribute to the analysis ‘as randomized’.

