12.1. Analysis Sets

All enrolled and treated subjects will qualify for the Full Analysis Set (FAS), the Per Protocol Analysis Set (PPS), the Safety Analysis Set and the Pharmacokinetic Analysis Set (PKS). The decision to exclude subjects from any of the analysis sets will be taken by the clinical study team before database lock and documented in the database lock minutes. Further details will be specified in the SAP.

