12.1.1. Full Analysis Set

The FAS will include all treated subjects for whom relevant post baseline efficacy and safety data have been collected.

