4.2 Patient disposition

The summary table for patient disposition will be presented in the following way:

The number of patients screened, the number of patients in the FAS, PPS, PKS and SAF analysis sets, completers and withdrawals with reason for withdrawal will be summarised with frequency and percentage by treatment.

The patient disposition will also be listed by patient.

The patients screened but not allocated to treatment will be presented with the reason(s) for screening failure in a listing.

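### Protocol and SAP both leave randomised-but-untreated patients out of the FAS in an unblinded trial, so exclusions can depend on the known arm; the risk falls mainly on Day 180 graft loss and survival

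*SAP*

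**What the plan says.** SAP 3.1 admits a patient to the FAS on one condition: "FAS will consist of all patients treated with any amount of study medication". It then analyses that patient in the randomised arm. Protocol 12.1.1 asks for more: "The FAS will include all treated subjects for whom relevant post baseline efficacy and safety data have been collected". Protocol 12.1 makes treatment a condition for all four analysis sets. Neither document defines a set of all randomised patients.

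Protocol 6.1.1 puts randomisation at the end of the screening visit, and 6.1.2 starts treatment at Visit 2, Day 1. SAP 2.3 states: "The study is an open-label study. The study is fully unblinded". On who may be left out, protocol 12.1 says: "The decision to exclude subjects from any of the analysis sets will be taken by the clinical study team before database lock". SAP section 3 gives the same timing: "The analysis sets will be determined at the data review prior to database lock".

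The primary endpoint is analysed on the FAS and PPS (SAP 4.6.1). Graft loss, transplant glomerulopathy, AMR resolution and survival at Day 180 are reported on the FAS (SAP 4.6.2). The disposition table in SAP 4.2 covers "The number of patients screened, the number of patients in the FAS, PPS, PKS and SAF analysis sets", then completers and withdrawals with reasons. It has no count of patients randomised. SAP section 5 declares a change to the PK set but none to the FAS, and the change log in section 10 does not mention one.

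**The concern.** Leaving out patients who never start treatment is harmless when the decision to start cannot depend on the allocation. Here it can. The arm may be known before the first treatment, and the arms ask very different things of the patient: one short infusion, or 5 to 10 PE sessions. Protocol 4.5 lets subjects withdraw at any time and lets investigators withdraw them. Protocol 4.1 foresees an eligible subject who is not given imlifidase and is later rescreened.

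If non-starters are more common in one arm, or differ in prognosis, the two FAS groups are no longer the groups that randomisation made. The trial tests no hypothesis, so the harm is a distorted estimate in a small table, not a false-positive rate. Without a randomised denominator, a reader of that table cannot easily judge the distortion.

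**Working it through.** **1. Who is in the FAS under each definition**

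| Patient | Protocol 12.1.1 | SAP 3.1 | All randomised |
|---|---|---|---|
| Randomised, never treated | out | out | in |
| Treated, no relevant post-baseline data | out | in | in |
| Treated, with post-baseline data | in | in | in |

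The first row carries the arm-dependent exclusion, and the two documents agree on it. They differ only in the second row, where the SAP is the more inclusive.

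**2. The plan's own figure**

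Protocol 12.4 and SAP 2.2 expect a 95% CI about 8 points wide for the difference in DSA reduction. They use SDs of 6% and 4% from two earlier studies and 20 + 10 patients.

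Width = 2 × t(0.975, n1 + n2 − 2) × SD × √(1/n1 + 1/n2).

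With SD 5 (the mean of 4 and 6) and t(28) = 2.048: 2 × 2.048 × 5 × √(1/20 + 1/10) = 7.93. With the root-mean-square SD of 5.10 it is 8.09. The figure reproduces.

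**3. Precision after exclusions**

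The counts are assumed, because the documents give none. SD is 5.

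| Imlifidase + PE | Width (points) |
|---|---|
| 20 + 10 | 7.93 |
| 20 + 9 | 8.24 |
| 20 + 8 | 8.60 |
| 20 + 7 | 9.04 |
| 18 + 10 | 8.11 |

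Precision is a minor matter.

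**4. DSA primary endpoint**

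If k excluded patients differ from those retained by D points, the arm mean moves by kD/10 (PE) or kD/20 (imlifidase). For an assumed D = 20, that is 2.0 or 4.0 points in PE for k = 1 or 2, and 1.0 or 2.0 points in imlifidase.

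These values exist only for patients who were sampled. The endpoint needs a baseline value and a value within 5 days of treatment start, and missing values are not imputed (SAP 4.1.4). A never-treated patient would usually contribute nothing under either FAS, so the computed primary result hardly changes.

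**5. Day 180 proportions**

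Suppose one PE patient is excluded, r of the other nine lose the graft, and x is 1 if the excluded patient loses it and 0 if not. The error in the PE proportion is r/9 − (r + x)/10.

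| | r = 0 | r = 1 | r = 2 |
|---|---|---|---|
| x = 1 | 0/9 − 1/10 = −10.0 points | 1/9 − 2/10 = −8.9 | 2/9 − 3/10 = −7.8 |
| x = 0 | 0 | 1/9 − 1/10 = +1.1 | 2/9 − 2/10 = +2.2 |

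For one excluded imlifidase patient the extreme is 0/19 − 1/20 = −5.0 points. With x = 0 and r = 1 it is 1/19 − 1/20 = +0.3 points.

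**The case against.** The strongest reply is that the problem may never arise and that the remedy could add little.

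- **Likelihood.** Entry requires willingness to comply and excludes patients who cannot tolerate plasmapheresis. PE follows each site's usual practice. Protocol 1.3 treats delay as harmful, which suggests a short gap between randomisation and treatment. The documents report no untreated randomised patient. This stands: the risk is potential and its size unknown.
- **Visibility.** A reader might infer that such losses would be hidden. The documents do not support that. SAP 4.2 gives withdrawals with reasons by treatment, Table 14.1.1 and Listings 16.1.1.1 and 16.1.1.2 carry no FAS restriction, and exclusions go into the database lock minutes. What is missing is an explicit randomised denominator and an untreated count.
- **The undeclared difference.** A reader might infer that the SAP's unannounced wording creates the exclusions. It does the opposite and admits more patients. Protocol 12.1 also leaves further detail to the SAP. Still, removing an inclusion condition is a change, and protocol section 13 requires changes to be documented.
- **Obtainable outcomes.** A reader might take protocol 4.5 to secure Day 180 status for everyone. It asks for a last visit only where possible, and that visit may fall well before Day 180. A patient who declines and leaves may have unknown status.
- **An undefined clock.** The DSA endpoint and graft loss are timed from treatment, which a never-treated patient lacks, and a rescreened patient could be counted twice. Both objections are sound, so any redefinition has to settle them.
- **The extreme case.** The 10-point error needs an excluded PE patient who is followed, loses the graft and is the arm's only event. Exact 95% CIs for 0/9 and 1/10 are about 0 to 34% and 0.3 to 45%, so chance alone covers the difference. This limits the weight of the point but does not remove a systematic route to selection.

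**Conclusion.** The point holds for the treated-only rule, which both documents share. In a fully unblinded trial that randomises at screening and treats at Visit 2, it lets FAS membership depend on the known arm. One excluded patient is 10% of the PE arm or 5% of the imlifidase arm. For PE graft loss with up to two other events in that arm, the error ranges from +2.2 to −10.0 points per excluded patient. This assumes that such a patient exists and that the outcome is known, and the documents establish neither.

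The risk lies mainly with graft loss and survival at Day 180. Glomerulopathy and AMR resolution also depend on a Day 180 biopsy, which an untreated patient who has left would probably not have. The documents do not support reading this as a material threat to the DSA primary result or to the planned CI width. The SAP's omission of the protocol's post-baseline-data condition is a separate documentation gap.

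**What to change.** In SAP 3.1, define the FAS as all randomised patients, analysed as randomised, and add these rules:

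- Each person is counted once, under the first randomisation if rescreened.
- For never-treated patients, graft loss and survival are counted from the date of randomisation.
- Unknown Day 180 status is reported as unknown, by arm.
- Never-treated patients enter the DSA endpoint only if they have the required samples.

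In Table 14.1.1, add the numbers randomised and randomised-but-untreated, by arm and with reasons. In SAP section 5, list the FAS change, including the removal of the protocol's post-baseline-data condition.

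The cost is SAP wording and a few table rows. The downside is that some untreated patients may have missing DSA or Day 180 data. The current SAP is dated August 2022, late against the protocol's recruitment and follow-up timeline, so status not already collected may be hard to recover. If every randomised patient was treated, membership is the same as under SAP 3.1 as it stands, and the new rows show it. Label: cheap improvement.
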